
On August 2018, the NHS DPP released a new framework for 'Healthier You: NHS Diabetes Prevention Programme'. The aim of the new framework is to expand the programme and to improve take-up and adherence to the DPP, including better targeting of the working age population and addressing delays associated with courses in rural areas.

The new framework also includes implementation of digital support for diabetes prevention alongside existing face-to-face provision, which has the potential to be one of the largest implementations of a digital programme in the NHS. Recruitment onto the new framework will start in August 2019, covering 45% of the sites in England, with the remaining 55% covered in 2020.

For operational reasons the DPP team re-procured the DPP intervention before the digital pilot could report. Therefore, the initial re-procurement focused mainly on face to face prevention programmes. However, all five of the new framework providers have been required to offer a digital prevention programme to people who decline invitation to the face-to-face programme. Once the results from the Digital DPP pilot are released, the DPP management team might decide to open up choice between face-to-face or digital intervention.

Aims and objectives

The overall aim of the DIPLOMA research programme is to provide a comprehensive assessment of the implementation, delivery and outcomes of the NHS DPP to inform commissioning.

The individual work package aims are as follows:

Work package 1 Access and Inequality

To assess whether sociodemographic factors influence access to the NHS DPP, and to explore the experience of patients and professionals in accessing the NHS DPP

Work package 2 Implementation

To assess the process of implementation of the NHS DPP, and explore the barriers and facilitators that affect the implementation of the NHS DPP

Work package 3 Service Delivery and Fidelity

To assess the theory, techniques and content of the NHS DPP, examine variation in delivery, and report the extent to which the NHS DPP is delivered with fidelity

Work package 4 Outcomes

To assess what outcomes participants achieve in the NHS DPP, and whether outcomes vary by services delivered and patient characteristics

Work package 5 Comparative Effectiveness

To assess whether the NHS DPP is more effective than usual care in reducing conversion of non-diabetic hyperglycaemia to diabetes, eventually reducing diabetes prevalence in England

Work package 6 External Validation

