- b) ELSA adults aged 50+ with 457 wave 2 participants, 1,297 wave 4 participants, 1,315 wave 6 and 806 wave 8 participants with HbA1c between 42-47 mmol/mol
- c) NDA (comparative observable factors e.g. age, gender, IMD, comorbidity; flags for non-diabetic hyperglycaemia)

Research question WP 1.2: Are there inequalities in the referral of patients to the NHS DPP?

Once a diagnosis of non-diabetic hyperglycaemia has been made, the GP may or may not refer the patient to NHS DPP. This decision to refer may be influenced by both the GP and patient, and may be related to patient or professional perceptions of the value of the service.

Method: We will compare the observable characteristics of patients referred to the NHS DPP in the Minimum DataSet (MDS) to patients identified with non-diabetic hyperglycaemia in the NDA dataset and those in surveys using analogous methods as those described in WP 1.1. The MDS contains information that providers of the DPP are contractually obliged to collect in order to receive financial reimbursement. It contains dates and sources of referrals and information about subsequent programme attendances, as well as participant outcome measures, as recorded by the providers of the programme.

Research question WP 1.3: Are there inequalities in attendance and completion of the NHS DPP?

Following a positive identification of non-diabetic hyperglycaemia, patient uptake and adherence to the NHS DPP intervention may vary. We can examine this in the MDS, using relevant codes for 'referral to the NHS DPP intervention', 'intervention started', 'declined' and 'completed'.

Method: Using MDS data (observable patient characteristics e.g. age, gender, IMD, co-morbidities). for those referred and on the programme we will compare the characteristics of patients and how this varies with course uptake and completion, the characteristics will be compared to patient characteristics in the NDA and survey datasets to understand at what point the characteristics of patients begins to change.

Research question WP1.4 What is the experience of patients and professionals in accessing the NHS DPP?

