The purpose of the scoping study is to identify factors that may influence access to NHS DPP, to help us design a questionnaire for the validation study. Method: we will use data from the qualitative interviews with patients and health professionals in the Access work package to identify important potential influences on access. We will use this to draw up suitable questions, in discussion with patients and clinicians on the Research Advisory Group. We anticipate that this is likely to include factors such as health status, comorbidities, motivation to improve health, health literacy and competing demands (e.g. employment, caring responsibilities).

Step 2: Questionnaire survey

We will undertake a short questionnaire survey of 400 patients (using post, telephone and online methods), to collect data on key patient factors (identified from the scoping study) that are likely to influence the offer and take-up of referral to the NHS DPP (i.e. whether 'NHS DPP referred' patients are referred to and attend the programme), but that are unavailable in routine datasets.

The purpose of the survey is:

- (a) To delineate the role psychological and social factors play in access inequalities, and identify factors potentially addressable by targeted interventions or programme modifications;
- (b) To determine the relative influence of and overall influence of these factors on participation;
- (c) To combine the results with analyses of CPRD, the minimum dataset, and other data sources to assess the extent to which associations between referral, programme attendance, and development of diabetes are confounded with patient characteristics and to adjust the associations for those factors.

The sample will consist of up to 30 patients from each of 20 practices. A suitable approach to sample size estimation for building regression models is to include 20 cases per parameter to be estimated. Our questionnaire includes 20 predictors (some of the questions will be combined into composites), giving us a recruitment target sample size of 400. To achieve this we are approaching a total of 600 patients.

Practices will produce a list of people at risk of diabetes who have been referred to DPP at least 3 months ago. After checking the list, practices will use a randomisation list provided by researchers to randomly select patients in a 1:1 ratio according to whether they are:

- (a) 'NHS DPP non-attenders', referred to NHS DPP but who did not attend any sessions

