- (b) NHS DPP attenders.

In practices where DPP attendance is not recorded we will send questionnaires to referred patients and ask about NDPP attendance as part of the questionnaire, to place each individual responder in the relevant attenders or non-attenders group. On average, 50% of people referred to DPP attend the programme, so this approach should result in roughly equal groups. Additionally, in practices which hold clinics to review patients at risk of diabetes, study information can be provided to eligible patients.

A high recruitment rate is essential to minimise bias in the validation sample. The questionnaire will be as short as practicable. We will use intensive recruitment and collection methods, working closely with professionals and the NIHR CRN locally, piloting the questionnaire prior to use with patients, and using financial incentives to patients and practitioners, ¹¹⁶¹¹⁷ aiming for a 70%-80% recruitment rate.

The high response rate required means that this work-package is 'high-risk'. If we manage to reach this target then our findings in this section will augment the quality of the analyses in work-package 5 and 7. However, the analyses in those work packages are not dependent on the success or otherwise of this survey. If a lower response rate is evident, the data will still be of considerable value, as it will allow us to examine the role of psychological and social factors in access inequalities, and study the relative influence of GPs and patient self-selection on NDPP participation.

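### WP6 splits referred patients into any session versus none, with no status for people still waiting, so late starters are modelled as non-attenders

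*Protocol*

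**What the plan says.** The rule is in the protocol, Work package 6, Step 2 (Questionnaire survey). Practices compile a "list of people at risk of diabetes who have been referred to DPP at least 3 months ago", with no upper limit on time since referral. From that list they "randomly select patients in a 1:1 ratio according to whether they are" attenders or non-attenders, and a non-attender is someone "referred to NHS DPP but who did not attend any sessions".

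Where a practice does not record attendance, referred patients are asked about it in the questionnaire, "to place each individual responder in the relevant attenders or non-attenders group". The protocol expects roughly equal groups there because "On average, 50% of people referred to DPP attend the programme".

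The survey has three purposes: (a) to show how psychological and social factors shape unequal access and which of them could be acted on, (b) to measure the relative and overall influence of these factors on participation, and (c) to support confounding adjustment with other data. The Analysis paragraph models attendance on patient factors by logistic regression and derives a propensity score for attending.

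Elsewhere the protocol recognises that starting can be slow. The section on the digital programme gives "addressing delays associated with courses in rural areas" as an aim of the new framework, and the WP2 amendment and the WP9 rationale say much the same. None gives a duration.

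**The concern.** Having attended no session at a given date can mean several things: the patient declined, never responded, was not contacted, or accepted and is waiting for a course. The WP6 rule merges them. If some labelled non-attenders will later attend, they resemble attenders on the factors being studied, and real differences between the groups shrink towards no effect.

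Time since referral adds to this. Someone referred 3 months ago has had less chance to start than someone referred a year ago, and nothing in the described models accounts for it.

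Purposes (a) and (b) are at stake. Declining and waiting call for different programme changes, and a merged group cannot separate them. The grouping is fixed when practices draw the sample and when the questionnaire is completed. A later analysis plan could not recover the distinction if status and referral date were never collected.

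**Working it through.** **The plan's own figures.** 20 predictors × 20 cases per parameter = 400. 20 practices × 30 patients = 600. The target needs 400/600 = 66.7% response; the stated 70% to 80% would give 420 to 480. These figures reproduce. The point concerns the group definition.

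**How the rule classifies a patient referred 3 or more months ago**

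| Situation at survey | Group under the rule |
|---|---|
| Attended one or more sessions | Attender |
| Declined or never responded | Non-attender |
| Booked, or waiting for a first session | Non-attender |

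**Dilution, reading 50% as the eventual attendance rate.**

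Inputs:
- Eventual attendance 0.50 (protocol).
- w = share of eventual attenders not yet started at survey; assumed 10%, 20%, 30%, because the protocol gives no figure.
- Factor prevalence 50% in attenders and true odds ratio 2.0 (both assumed). The odds in settled non-attenders are then 1/2, so prevalence is 1/3.
- Those waiting resemble attenders on the factor (assumed).

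Share of labelled non-attenders who are future attenders: c = 0.5w / (0.5 + 0.5w).

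Factor prevalence in labelled non-attenders: p = (1 − c)/3 + c/2.

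The odds in attenders are 1, so the observed odds ratio is (1 − p)/p.

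| w | c | p | Observed odds ratio (true 2.0) |
|---|---|---|---|
| 10% | 0.05/0.55 = 9.1% | 0.348 | 1.87 |
| 20% | 0.10/0.60 = 16.7% | 0.361 | 1.77 |
| 30% | 0.15/0.65 = 23.1% | 0.372 | 1.69 |

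**Alternative parameterisation.** Let v be the share of labelled non-attenders who are waiting and q the share of those who would go on to attend. Then p = (1 − vq)/3 + vq/2.

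| v | Odds ratio, q = 1 | Odds ratio, q = 0.5 | Power, q = 1 |
|---|---|---|---|
| 0% | 2.00 | 2.00 | 92% |
| 10% | 1.86 | 1.93 | 86% |
| 20% | 1.73 | 1.86 | 77% |
| 30% | 1.61 | 1.79 | 65% |

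Power is for a single unadjusted factor, 200 per group, two-sided 5%. The two approaches agree on direction and rough size. Neither shows how many people actually wait.

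**The case against.** The strongest reply is that the harm is assumed. No passage says delays exceed 3 months. The minimum interval keeps the newest referrals off the list, and with no ceiling many listed patients may have been referred long before. This stands as a limit on size: the shares above are illustrations. It does not remove the gap, because the protocol does not tie the 3 months to any usual time to first session.

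A reader might infer that the plan treats waiting as a patient's decision not to attend. The text does not support that. WP6 speaks of barriers to access and of influences on both offer and take-up, and it names GP influence alongside self-selection. Failing to reach a session because of supply is arguably part of the access question. Even so, supply should be distinguishable from patient factors.

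A reader might also infer a false rural versus urban difference in attendance. Where attendance is recorded, sampling is 1:1 within each practice, which fixes the attender share at about half in every practice selected. Such a gap between practices could arise only where attendance is self-reported, and the number of those practices is unknown.

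Finally, the questionnaire is a separate document and may already ask about waiting. The protocol's description gives two destinations only.

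**Conclusion.** The point holds as a limited misclassification built into the sampling rule. Anyone still waiting for a first session is modelled as a non-attender, and time since referral is not controlled. If 10% to 30% of eventual attenders had not started at survey, and they resemble other attenders, a true odds ratio of 2.0 would read about 1.87 to 1.69. If few people wait beyond 3 months, the effect is negligible. The documents cannot settle which.

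The harm is mainly to purposes (a) and (b). It is tempting to conclude that WP5 and WP7 are compromised, since the WP6 factor and propensity scores are meant to support their adjustment. WP6 states, however, that those analyses do not depend on the survey. The main WP5 contrasts are before versus after the programme and referred versus not referred, not attenders versus non-attenders among those referred.

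**What to change.** 1. Add one questionnaire item recording whether the respondent is still waiting for, or booked on, a first session.
2. Record the referral date and include time since referral as a covariate in the attendance models.
3. Report those waiting as a separate descriptive group.
4. Repeat the attender versus non-attender models and the propensity model without them, as a sensitivity analysis.

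The exclusion belongs in a sensitivity analysis. Some people who say they are waiting 3 or more months after referral may never attend, so redefining non-attenders by stated intention could exaggerate the contrast.

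The cost is one item, one model parameter and a smaller sample in the sensitivity analysis. Under the plan's own rule, 21 parameters × 20 = 420 respondents, which equals the lower end of its response target (70% of 600). With 200 labelled non-attenders, removing 9.1%, 16.7% or 23.1% leaves about 182, 167 or 154.

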Analysis: Descriptive statistics will be used to characterise the groups of people who attend, and do not attend, the DPP across a range of demographic, attitudinal and psychological factors; and comparisons will be made to available national data (e.g. from the DPP "minimum dataset"). We will use univariate and multivariate logistic regression methods to estimate and compare the role of the various factors in influencing attendance at the NHS DPP intervention. We will also compute a propensity score for each individual representing their probability of attending given their particular combination of factors, to provide a picture of the extent to which these factors as a whole are associated with attendance. The individual factor and propensity scores will further be used in combination with analyses of CPRD, the minimum dataset, and other data sources to assess the extent to which any observed associations between DPP referral and attendance and subsequent development of diabetes are confounded with demographic differences and to adjust the associations for those differences. These results will further feed into the health economics analysis of the cost-effectiveness of the programme, particularly in relationship to estimating effectiveness in patient sub-populations.

Work package 7 - Comparative Long-term Cost Effectiveness ([name] and [name])

Aims: To assess whether the NHS DPP is cost-effective compared to usual care in terms of long-term costs and benefits

Rationale: As with work package 5, commissioning of the NHS DPP will also be dependent on a rigorous demonstration of cost-effectiveness. Diabetes is associated with compromised quality and length of life and significant long-term health care utilisation. Effective prevention has the potential to generate health benefits and significant cost-savings over the longer term. This work package will utilise economic modelling to explore the longer term costs and benefits of the NHS DPP.

Overview of methods: This work package will estimate the overall cost effectiveness of the NHS DPP taking account of the costs incurred by commissioners to deliver the programme and the long-term health benefits for participants and non-participants. It will draw together the findings of the other work packages and use an economic model to summarise the overall cost-effectiveness of the programme as implemented and identify major opportunities for enhancing its cost effectiveness.

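### WP6 selects patients 1:1 by attendance within practices that record it, but the named logistic regression takes no account of practice, so factors that cluster by practice are shrunk when influences are compared

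*Protocol*

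**What the plan says.** All of this is in the Protocol, Work package 6 - Validation Study.

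- **Sampling (Step 2: Questionnaire survey).** From lists of patients referred at least three months earlier, "practices will use a randomisation list provided by researchers to randomly select patients in a 1:1 ratio according to whether they are" non-attenders or attenders.
- **Exception (same section).** "In practices where DPP attendance is not recorded we will send questionnaires to referred patients", and attendance is then taken from the patient's own answer. These practices are not sampled by outcome. The protocol puts average attendance among referred patients at 50% but gives neither its spread across practices nor the share of practices that record it.
- **Size (same section).** "The sample will consist of up to 30 patients from each of 20 practices". The rule is to "include 20 cases per parameter to be estimated", with 20 predictors, "giving us a recruitment target sample size of 400". "To achieve this we are approaching a total of 600 patients". Practice is not among the parameters counted.
- **Analysis.** "We will use univariate and multivariate logistic regression methods to estimate and compare the role of the various factors in influencing attendance". A propensity score for attending is also to be computed. No practice term, stratification, conditioning or weighting is named.
- **Purpose.** One of the three stated purposes of the survey is to determine the relative influence of the factors on participation, so the ordering of effects is an intended output.

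**The concern.** Selecting equal numbers of attenders and non-attenders inside a practice makes a case-control sample stratified by practice. A practice whose referred patients have, say, low health literacy contributes the same half-and-half split as every other practice, so the between-practice part of the association is forced to zero. A pooled model that ignores practice averages this artificial zero with the real within-practice effect.

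The shrinkage differs between factors. It depends on how much of a factor's variance lies between practices, so the comparison of factors is distorted and not merely rescaled. Practices that survey unselected patients do not have this problem, which means that one model would pool two sampling schemes without a rule for doing so.

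The propensity score is affected too. In the 1:1 practices its baseline is set by the sampling and not by how often that practice's referred patients attend.

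**Working it through.** **The plan's own figures.** 20 cases × 20 predictors = 400; 20 practices × 30 patients = 600. Both reproduce. They imply a response of 400/600 = 66.7%.

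**Size of the shrinkage.** Give a factor total variance 1, of which a share ICC lies between practices. Let β be its true log odds ratio, the same within and between practices.

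- All practices 1:1: the within part (share 1 − ICC) carries β and the between part (share ICC) carries 0. The pooled estimate is about β × (1 − ICC).
- Half the practices 1:1: averaging β × (1 − ICC) and β gives about β × (1 − ICC/2).
- No practice 1:1: no shrinkage from this source.

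**Check by simulation.** Inputs: a clustered factor with true odds ratio 1.5 per SD and a nearly unclustered one with 1.4 (ICC 0.02); practice intercept SD 0 or 0.5; 10 attenders and 10 non-attenders per 1:1 practice, or 20 unselected patients; 1,500 practices to isolate bias. All of these are assumptions except the 20 responders per practice, which is 400/20. The entries are the clustered factor's estimated log odds ratio divided by the truth, from logistic regression without practice.

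| ICC | 1 − ICC | All 1:1 | 1 − ICC/2 | Half 1:1 |
|---|---|---|---|---|
| 0.05 | 0.95 | 0.97 | 0.975 | 0.98–0.99 |
| 0.1 | 0.90 | 0.91–0.94 | 0.95 | 0.92–0.96 |
| 0.2 | 0.80 | 0.76–0.82 | 0.90 | 0.83–0.91 |
| 0.3 | 0.70 | 0.69–0.72 | 0.85 | 0.82–0.89 |

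Simulation error is about 0.03 to 0.05. A separate simulation gave 0.95, 0.90, 0.80 and 0.70 with all practices 1:1, and about 0.86 at ICC 0.3 with half. In the all-1:1 runs at these ICCs the unclustered factor stayed at 0.94–1.01. With no practice 1:1 the clustered factor's ratio was 0.91–1.04, with no trend in ICC.

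**Effect on the ordering at the planned size.** 20 practices × 20 responders, 500 replicates, practice intercept SD 0.5. Share of samples in which the weaker factor (1.4) is ranked above the stronger (1.5):

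| ICC | All 1:1, practice ignored | All 1:1, practice fixed effects | Half 1:1, practice ignored |
|---|---|---|---|
| 0.02 | 31% | 32% | 32% |
| 0.1 | 41% | 35% | 33% |
| 0.2 | 46% | 28% | 42% |
| 0.3 | 62% | 32% | 45% |

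Chance alone accounts for roughly 31–32%. With practice fixed effects the clustered factor's odds ratio returns to 1.49–1.52. That result includes a 19/20 correction for the small-stratum bias of fixed effects.

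**A random intercept is not a repair.** If every practice is 50:50 by design, the sampled outcome has no between-practice variance. The estimated intercept variance is then zero and the model collapses to the one that ignores practice.

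**The case against.** - **The model is not called ordinary.** The protocol says logistic regression methods and excludes nothing; an analysis plan not shown could add a practice term. This stands in part. But the method as written has no such term, practice is missing from the parameter count, and the random-effects form named in WP4.5 would not help here. The list counts needed for weighting must also be kept at sampling and cannot be recovered by a later analysis plan.
- **A reader might infer that every practice is sampled 1:1.** The protocol exempts practices without attendance records, so the all-1:1 figures are the worst case.
- **A reader might infer that deprivation and ethnicity effects are the ones damaged.** WP6 does not name them as predictors. It speaks of demographic, attitudinal and psychological factors, and its examples (health status, motivation, health literacy, competing demands) may cluster little. Social gradients in uptake are examined on far larger data in WP1.3 and WP4. Socio-demographic factors are only a possible example.
- **A reader might infer that WP5 and WP7 are undermined.** The protocol says that those analyses do not rely on the survey. WP5 design 1 has deprivation in its own propensity model, and the main analysis of design 2 matches within practice.
- **A reader might infer a loss of power.** WP6 states no power target, so the issue is bias and ordering.
- **Chance already misorders close effects.** This is true: about a third of samples at odds ratios of 1.5 and 1.4. With half the practices 1:1 and an ICC of 0.1, the excess is negligible.
- **Average attendance is 50%, so 1:1 sampling keeps the baseline.** This holds on average but not for individual practices, whose attendance will vary.

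**Conclusion.** The point holds in a limited form. In practices sampled 1:1, the analysis as written shrinks each factor's log odds ratio by roughly its between-practice ICC. That is about 5% at 0.05, 10% at 0.1, 20% at 0.2 and 30% at 0.3 if all practices are 1:1, and about half as much if half are. The comparison of relative influence is biased against any factor that clusters by practice. It is close to unbiased among factors that do not.

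The size rests on assumptions that the documents do not settle: the ICCs, the share of practices that record attendance, equal within- and between-practice effects, and non-response that leaves the 1:1 balance about the same in every practice. At an ICC of 0.05 the bias is small. The harm is to WP6's own ranking and to an optional adjustment for other work packages. It is worth correcting because the remedy is standard and cheap.

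**What to change.** 1. Estimate and compare the factors by conditional logistic regression stratified by practice, across all practices. This is valid under both sampling schemes. Practice fixed effects are an alternative but carry a small-stratum bias (about 20/19 with 20 responders per practice). Under the protocol's own rule, 19 practice terms would raise the target to 20 × (20 + 19) = 780, whereas conditioning adds no estimated parameters. A random intercept alone should not be used.
2. State that practice-level influences on attendance cannot be estimated from the 1:1 practices.
3. Have each practice that records attendance return the numbers of attenders and non-attenders on its list. Fit the propensity score in a separate model weighted by the inverse of the sampling fractions, so that it refers to the referred population. Conditional regression does not itself give predicted probabilities.

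**Cost.** Some analysis wording and a few counts from lists that practices already produce. Factors constant within a practice drop out; 1:1 sampling has already removed them where it is used, but the unselected practices lose that information. Estimates of clustered factors become more variable. With all practices 1:1, the SD of the log odds ratio under fixed effects was 0.127 against 0.094 at ICC 0.3, and 0.114 against 0.111 at ICC 0.02.

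### WP6 pictures the joint association of about 20 factors with attendance by propensity scores fitted to the same 400 or so respondents; read uncorrected, that picture is biased upward

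*Protocol*

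**What the plan says.** Protocol, Work package 6, Step 2 (Questionnaire survey) sizes the survey by a rule of thumb, which is to "include 20 cases per parameter to be estimated". It adds that "Our questionnaire includes 20 predictors", "giving us a recruitment target sample size of 400". On numbers invited it says: "To achieve this we are approaching a total of 600 patients". Where attendance is recorded, practices will "randomly select patients in a 1:1 ratio according to whether they are" non-attenders or attenders. Where it is not recorded, equal groups are expected because "On average, 50% of people referred to DPP attend the programme". The same section describes the surveyed factors as ones that routine datasets do not hold. The second of its three listed purposes is to determine the relative and the overall influence of these factors on participation.

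The Analysis paragraph plans univariate and multivariate logistic regression for attendance. It then computes a propensity score for each individual "to provide a picture of the extent to which these factors as a whole are associated with attendance". It goes on: "The individual factor and propensity scores will further be used in combination with analyses of CPRD, the minimum dataset, and other data sources", in order to assess confounding and adjust for it.

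The paragraph names no separate sample, cross-validation, optimism correction or joint test for the summary of overall association.

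**The concern.** The regression coefficients are chosen to fit the attendance pattern of these respondents, including its chance part. When the resulting scores are laid out by group in the same respondents, attenders score higher than non-attenders by construction, whether or not any factor matters. With about 200 people per group and at least 20 fitted terms, the chance part is not negligible.

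At stake is the survey's second purpose. The overall influence of these psychological and social factors on participation would be reported as larger than it is, and a weak or absent influence could be taken for a real one.

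**Working it through.** **1. The plan's own figures.** 20 predictors × 20 cases = 400. 20 practices × 30 patients = 600 approached. Both reproduce. In a 1:1 sample, 400 people give about 200 per group, so 200 / 20 = 10 per parameter in the smaller outcome group. The rule of 20 counts everyone.

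**2. Where the score can be fitted.** The factors are absent from routine data and the protocol names no second source. That the score is fitted and read in the same respondents is therefore an inference, though no other reading is offered.

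**3. Hand check with no true association.** For a linear discriminant with p unrelated predictors, the expected squared standardised distance between groups in the fitting sample is about p × (1/n1 + 1/n0) = 20 × (1/200 + 1/200) = 0.20. The standardised difference is then √0.20 = 0.447, and the AUC about Φ(0.447/√2) = Φ(0.316) = 0.624. For R-squared, the expected likelihood-ratio chi-squared is about 20, so Nagelkerke R² ≈ (1 − exp(−20/400)) / (1 − 0.5²) = 0.0488 / 0.75 = 0.065.

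**4. Simulation.** Logistic regression was fitted to 400 people on 20 independent predictors. Each fitted model was scored in the same 400 and in 2,000 new people. There were 2,000 runs for the null and 1,000 for each assumed true association. Brackets hold 95% of runs.

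| True association (linear-predictor SD, assumed) | AUC, same people | AUC, new people | Joint likelihood-ratio test rejects at 5% |
|---|---|---|---|
| None | 0.626 (0.588–0.669) | 0.50 (0.47–0.53) | about 6% |
| Weak, 0.3 | 0.651 (0.608–0.697) | 0.546 (0.510–0.579) | 39% |
| Modest, 0.5 | 0.682 (0.632–0.729) | 0.597 (0.560–0.628) | 85% |
| Stronger, 0.8 | 0.735 (0.687–0.781) | 0.672 (0.640–0.700) | 100% |

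In the null case the standardised difference in score is 0.46 (0.32–0.62) and Nagelkerke R² is 0.068, in line with step 3. Observed attendance is 34% in the lowest fifth of the score and 66% in the highest, although no factor matters.

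**5. Sensitivity of the null AUC.** Binary predictors: 0.626. At the 70%–80% recruitment rate aimed for, 420 respondents (600 × 0.70) give 0.624 and 480 (600 × 0.80) give 0.615. With 300 respondents it is 0.645. With 25 model terms, as when some items have several categories, it is 0.642; with 10 terms, 0.587.

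**6. Reading the table.** The mean for a weak association (0.651) lies inside the null range, so the uncorrected picture separates the two poorly. The mean for a modest association (0.682) lies above that range. The inflation can be measured in two ways. At SD 0.5 the apparent AUC exceeds that of the fitted model in new people by 0.682 − 0.597 = 0.085. It exceeds the AUC of the true linear predictor, about 0.63, by about 0.05. At SD 0.8 the second gap is about 0.03 (0.735 against 0.70).

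**The case against.** **The protocol promises a picture, not a test.** It names no C-statistic, threshold or comparison of scores between groups, and a statistical analysis plan could add internal validation. This stands in part. A formal test of the fitted score between groups would be significant in every null run, but the protocol proposes no such test and should not be charged with one. What it does fix is the fitted score as the means of judging joint association, and that choice is biased upward if left uncorrected.

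**An all-null scenario is extreme**, since the factors are chosen from qualitative work as likely influences. That is fair, and it is why the weak and modest scenarios matter. The inflation is smaller there but still present.

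**The multivariate logistic model already yields the joint likelihood-ratio statistic.** It does, at close to its nominal error rate. The paragraph simply does not name it as the summary.

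Two stronger readings are tempting:

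- A reader might infer that WP6 cannot tell no confounding from moderate confounding. The figures do not bear this out: at SD 0.5, 83% of apparent AUCs exceed the null 95th percentile, and at SD 0.8 all do. Moreover, the WP6 rationale defines a confounder as acting on both participation and progression to diabetes, so separation on attendance alone does not measure confounding.
- A reader might infer that over-fitted scores corrupt the adjustment in WP5 and WP7. The protocol does not fix how the scores would be combined with other data, so no bias in those estimates can be shown. Step 2 says those analyses do not depend on the survey, and WP5.2 design 2 plans its own methods for unmeasured confounding. Optimism in discrimination is also not the same as bias in an adjusted effect.

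**Conclusion.** The point holds for the summary of overall association with attendance, and only for that. Read without correction in the respondents used for fitting, the scores show an AUC of about 0.63 when nothing is associated with attendance, and overstate weak and modest associations by about 0.10 (0.65 against 0.55) and 0.08 to 0.09 (0.68 against 0.60) relative to new people. No association and a weak one are poorly distinguished; moderate and strong ones remain visible. The sample-size arithmetic itself is sound.

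The figures assume independent predictors with one parameter each, no clustering by practice, no missing data and equal groups. The linear-predictor SDs are assumed, since the protocol gives no expected strength. The documents do not show harm to WP5 or WP7, and they give no basis for requiring penalised or out-of-fold scores there.

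**What to change.** In the WP6 Analysis paragraph, state that the overall association of the factors with attendance will be reported by two things: the joint likelihood-ratio test of all factors in the multivariate model, and a C-statistic and R-squared corrected for optimism by bootstrap or cross-validation. Add that the strength of association will not be read from the uncorrected in-sample scores. If the scores are displayed, put the corrected index beside them.

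The cost is a little more analysis and no added data. The reported association will be smaller. The change removes the overstatement but adds no information: at 400 respondents the joint test detects a weak association (SD 0.3) in only about 39% of runs, so a non-significant result should not be reported as absence of influence.
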